6.1 Risks

The risks related to the research include bruising and pain at the site of venipuncture for blood draws. Baseline blood draw will be collected as part of their routine care visit and the blood draw at 1- and 6-months post-immunization are research-related blood draws that will be done by a trained phlebotomist.

In addition, the research carries a minimal risk of breach of confidentiality, with multiple safeguards in place to protect subjects' privacy. Gout and optic ischemic neuropathy are overall rare and not causally linked to the Shingrix vaccine; therefore, they are not noted as risks.

Additional risks that are part of standard of care and therefore not part of research include vaccine-related reactions. Risks from the Shingrix vaccine include injection site adverse events: pain (78.0%),

redness (38.1%), and swelling (25.9%). Other possible general adverse reactions include myalgia (44.7%), fatigue (44.5%), headache (37.7%), shivering (26.8%), fever (20.5%), and gastrointestinal symptoms (17.3%).

Risks will be minimized by performing blood draws at the same time, when possible, as blood draws required for clinical care. Multiple safeguards, including a password protected computer to store the database, will be used to protect subjects' privacy.

Risks from the vaccine will also be mitigated by strict eligibility screening, which includes excluding subjects with a history of allergy to a zoster vaccine. At the time of obtaining informed consent, patients will be informed of the risks associated with the vaccine and will be provided a 24-hour number to study staff or the Gastroenterology fellow on-call for further management if reactions occur.

6.2 Potential Benefits

There are no direct benefits to subjects from participating in the study.

Societal benefits include providing data on the effectiveness of the Shingrix vaccine in patients on immunosuppressants. The data from this pilot study may be used to guide larger more powered studies in the future. The data from our study may also provide reassurance to patients and providers that that Shingrix is safe in a real-world setting for patients on immunosuppressants.

6.3 Analysis of Risks in Relation to Benefits

The risks of this study are minimal and are all sufficiently mitigated. While there is no direct benefit in this study, there are benefits to society. Therefore, with risks minimized, the risk to benefit ratio is favorable.

7 Study Subject Selection

7.1 Subject Inclusion Criteria

In order to be eligible to participate in this study, an individual must meet all of the following criteria:

- Age 18 or older
- Proof of primary varicella infection (chicken pox) either by appropriate history or, if history is atypical or mild, a positive VZV IgG antibody level
- Patient has a history of UC diagnosed by standard clinical, radiographic, endoscopic, and histopathologic criteria.
- Patient is receiving one of the following treatments for their UC
 - Tofacitinib monotherapy
 - Anti-TNF monotherapy (adalimumab, golimumab, infliximab)
 - Anti-TNF monotherapy plus a thiopurine (6 mercaptopurine, azathioprine)
 - No therapy or 5-aminosalicylates only if 50 years or older. (Individuals younger than 50 years, on no therapy or on 5-aminosalicylates will have to be immunosuppressed to fall under this category)

7.2 Subject Exclusion Criteria

An individual who meets any of the following criteria will be excluded from participation in this study:

- Previous receipt of any HZ vaccine
- Allergy to zoster vaccine or a component of the vaccine
- Other underlying chronic medical conditions that are immunosuppressive or could affect immunogenicity to vaccines (HIV, transplant recipient on anti-rejection drugs, rheumatoid arthritis, psoriasis etc.)
- History of herpes zoster infection or post herpetic neuralgia
- Patient cannot or will not provide written informed consent
- Patient is on a non-licensed or experimental immunomodulator
- Patient is on methotrexate
- Patient is on steroids
- Patient has received immunoglobulin therapy or blood products with the past month
- Patient is pregnant or lactating

8 Study Intervention

The study intervention Shingrix is an adjuvanted recombinant vaccine approved by the Food and Drug Administration in 2021 for the prevention of herpes zoster in immunosuppressed adults 18 years of age and older. The vaccine is administered as two doses (0.5ml each) intramuscularly according to the following schedule: A first dose at Month 0 followed by a second dose administered anytime between 2 and 6 months later.

The Shingrix vaccine will be administered to subjects as part of their standard clinical care. The vaccine will be purchased with funding from Pfizer and be provided to subjects at no cost.

9 Study Procedures

See the Appendix for the schedule of events.

Patients with UC who meet the inclusion and exclusion criteria specified above, including being on one of four treatment modalities, will be recruited from the Center for Digestive Diseases at Boston Medical Center, the Hospital of the University of Pennsylvania, or the University of Wisconsin Hospital and Clinics. All 4 treatment modalities are standard of care and will have been established outside of the study.

Research staff, including a clinical coordinator, will generate a list of eligible patients and email the subjects' primary gastroenterologist (who is also a member of the research staff) the name and next appointment date of these patients. Patients will only be approached for recruitment at their next usually scheduled clinic appointment. A handout of the risks and benefits of the clinically indicated vaccine (Shingrix) will be given to each patient during their visit for their review. Patients will have the opportunity to opt in, opt-out, or defer from enrollment early in the consent process upon review of the handout. Because the vaccine is standard of care, patients will retain the opportunity to get the vaccine even if they choose not to participate in the study.

If a patient elects to participate in the study, he/she will sign the consent, be entered into the study, and complete the initial study assessments. If a patient elects to defer enrollment at the time of their clinic visit, he/she will be instructed to call the 24-hour phone number if he/she decides to enroll in the study at a later date.

All patient data, including demographic information and study assessments, will be collected and entered into REDCap, a secure electronic data capture system. This will ensure the confidentiality and integrity of the data throughout the study. Only authorized research personnel will have access to the REDCap database to maintain participant privacy and comply with data protection regulations.

Subject contacts:

- #1 Baseline/Enrollment Visit 1 (Day 0): Subjects will have a comprehensive medical history and physical exam performed, including vaccination history and all medications over the past 30 days. They will also complete an SCCAI questionnaire. A baseline blood sample of approximately 20mL (4 tablespoons) will then be obtained. If proof of past varicella infection is met by appropriate history, subjects will receive the Shingrix vaccine indicated based on their vaccination history as recommended by their gastroenterologist; otherwise subjects will follow-up in 1 week to review confirmatory serology results and receive vaccine if indicated. The Shingrix vaccine will be given in a two-dose series (0.5 mL each) administered intramuscularly –first dose at Month 0 followed by a second dose anytime between 2 and 6 months later. Subjects will be instructed to call the study team for any concerns or any development of fever, chills, rash or other concerning symptom.
- #2- Follow up Visit 2 (approximately day 7): This visit is only needed for patients who require serologic confirmation of past varicella infection, therefore patients who meet proof for past varicella infection by appropriate history do not require serologic confirmation and will NOT be scheduled for this visit. Subjects will review results of the VZV antibody level test with their provider. If VZV antibody levels are positive, subjects will receive the Shingrix vaccine indicated based on their vaccination history as recommended by their gastroenterologist. Subjects will be instructed to call the study team for any concerns or any development of fever, chills, rash or other concerning symptom.
- #3 Follow up Phone Call 1 (approximately day 14): Subjects will receive a follow-up phone call to identify any adverse effects including fevers or chills, rash, and visits to the emergency room or to their primary care physicians. They will also be reminded about their follow up visit.
- #4 Follow up Visit 3 (approximately day 60, but can be up to day 180): Subjects will complete a SCCAI questionnaire, and information will be collected to identify any adverse effects including fevers or chills, rash, and visits to the emergency room or to their primary care physician. The 2nd dose of the Shingrix vaccine will be administered.
- #5 Follow up Phone Call 2 (approximately day 72): Subjects will receive a follow-up phone call to identify any adverse effects including fevers or chills, rash, and visits to the emergency room or to their primary care physicians. They will also be reminded about their follow up visit.
- #6 Follow up Visit 4 (approximately day 90): Subjects will complete a SCCAI questionnaire, and information will be collected to identify any adverse effects including fevers or chills, rash, and visits to

Version 1.7 06/22/2023

the emergency room or to their primary care physician. A blood sample of approximately 20mL (4 tablespoons) will then be obtained.

#7 - Follow up Visit 5 (approximately day 240): Subjects will complete a SCCAI questionnaire, and information will be collected to identify any adverse effects including fevers or chills, rash, and visits to the emergency room or to their primary care physician. A blood sample of approximately 20mL (4 tablespoons) will then be obtained.

The entire procedure will be identically performed at the additional sites outside of BMC. The total study duration will be about 2 years, and the subjects' duration of participation will range from 8 to 12 months, depending on when the 2nd vaccine dose is administered.

Participants will receive a total of \$50 in the form of reimbursement gift cards for their participation. A \$20 gift card will be given at the time of enrollment, and a \$30 gift card will be given at the 1-month post-immunization visit (follow-up visit 4).

All standard-of-care testing and procedures will be billed to the patient/patient's insurance. All initial research visits will be conducted as part of an already scheduled visit that the patient would be attending regardless of study participation; thus, the patient (or the patient's insurance) would cover the cost of this. At this visit, the patient will be vaccinated with a clinically indicated vaccine(s) that would be part of standard preventative care and have blood drawn. Patients with IBD generally have routine blood testing as part of their regular care. Given this, phlebotomy will be covered by the patient or their insurance, with the exception of the cost of the blood draws specifically for the research study (at follow up visits) which will be covered by research funding. The vaccine will be purchased with funding from Pfizer and be provided to subjects at no cost.

All blood samples will be processed (centrifuged, pipetted, and frozen) and stored at the research lab at BU/BMC medical campus located at [name]. Upon finishing enrollment, blood samples (coded only with subject ID and exclude any identifiable private information) will be released outside of the BMC/BU Medical Campus only to co-investigator [name] at the University of Wisconsin School of Medicine and Public Health. Samples will be stored and retained in a locked freezer until the end of the study.

If subjects wish to terminate their participation prior to the end of the study, they may do so by notifying their primary gastroenterologist or contacting the PI of the study via contact information included on their informed consent form.

10 Assessment of Safety and Data Safety Monitoring Plan (DSMP)

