	Appendix	
Sir	nple Clinical Colitis Activity Index (SCCAI)	27

1 List of Abbreviations

Abbreviation	Abbreviation definition
CMI	Cell mediated immunity
ELISPOT	Enzyme linked immunospot
IBD	Inflammatory Bowel Disease
ΙΕΝγ	Interferon gamma
HZ	Herpes Zoster
SCCAI	Simple Clinical Colitis Activity Index
TNF	Tumor necrosis factor
UC	Ulcerative Colitis
VZV	Varicella Zoster virus

2	Protocol	l Summary

_ Trococor Sammary	
Title:	Immunogenicity of herpes zoster subunit vaccine in ulcerative
	colitis patients treated with tofacitinib
Population:	UC patients on one of four treatment regimens as standard of care,
	who receive the Shingrix VZV vaccine, 100 patients, male + female,
	≥18 years old, no vulnerable populations
Intervention:	Each participant will be given two doses (0.5ml each) of the Shingrix
	vaccine, administered intramuscularly according to the following
	schedule: A first dose at Month 0 followed by a second dose
	administered anytime between 2 and 6 months later. The study
	population will generally include adult outpatient subjects with UC.
Objectives:	Change in CMI and VZV antibody concentration between pre-
•	immunization and at 1 month and 6 months post-immunization.
	Also monitoring for vaccine adverse effects over this time.
Design/Methodology:	Observational study without randomization and 4 study arms:
	Tofacitinib (10mg by mouth twice daily) monotherapy VS Anti-TNF
	monotherapy (adalimumab, golimumab, infliximab) VS Anti-TNF
	therapy with a thiopurine (6-mercaptopurine or azathioprine) VS no
	therapy or 5-aminosalicylates. Blood samples collected at clinic
	visits at enrollment, 1 month post-immunization, and 6 months
	•
	post-immunziation. If subject requires serologic confirmation of
	past VZV infection, an additional clinic visit 1 week after enrollment
	will be needed to follow-up on results of a confirmatory serology
	test.
Total Study Duration:	2 years.
Subject Participation Duration:	8-12 months.

3 Background/Rationale & Purpose

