4.1 Study Objectives

The primary objective of the study is to determine the immunogenicity of the herpes zoster subunit vaccine in ulcerative colitis patients on tofacitinib monotherapy compared to those on anti-tumor necrosis factor monotherapy, combination treatment with an anti-TNF agent and a thiopurine, and UC patients on 5-aminosalicylates or off therapy. Participants will be receiving the UC treatment regimens as standard of care prior to enrollment into the study. Immunogenicity will be evaluated by measuring humoral and cell mediated immunity in UC patients on tofacitinib who receive the two-dose herpes zoster vaccine. We will evaluate short term immunogenicity at one month after the second vaccination dose and sustained immunogenicity at 6 months post vaccination.

The central hypothesis of this proposal is that UC patients on tofacitinib will mount an adequate response to the Shingrix vaccine. We expect that the response will be slightly diminished compared to non-immunosuppressed IBD patients, comparable to those on anti-TNF monotherapy therapy and superior to those on anti-TNF therapy in combination with a thiopurine.

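### The printed draw days (about Days 90 and 240) fall 1 and 6 months after dose 2 only if dose 2 is given near Day 60, yet dose 2 may be as late as Day 180

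*Combined protocol and SAP*

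**What the plan says.** **Endpoints.** Section 4.1 sets the assessment times as "short term immunogenicity at one month after the second vaccination dose and sustained immunogenicity at 6 months post vaccination". Section 4.2.1 times the primary outcome, change in ELISPOT-measured cell-mediated immunity, to 1 month after the second dose. In Section 4.2.2, the sustained antibody outcome is explicitly 6 months after the second dose.

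**Dose 2.** Section 9 lists "Follow up Visit 3 (approximately day 60, but can be up to day 180"), and the Schedule of Events in the Appendix repeats that allowance.

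**Draws and call.** The later lines carry no such allowance and do not refer to dose 2:
- "Follow up Phone Call 2 (approximately day 72")
- "Follow up Visit 4 (approximately day 90): Subjects will complete a SCCAI questionnaire" (first post-vaccination blood sample)
- "Follow up Visit 5 (approximately day 240): Subjects will complete a SCCAI questionnaire" (second post-vaccination blood sample)

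The Schedule of Events prints the same three days, and Section 10.2 repeats Day 72 for the call.

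**Text that points to dose-2 timing.** Section 2 describes blood samples at "visits at enrollment, 1 month post-immunization, and 6 months" post-immunization, with no calendar day, and Sections 5 and 6.1 do likewise. Section 9 calls Visit 4 "the 1-month post-immunization visit (follow-up visit 4") and says that "duration of participation will range from 8 to 12 months, depending on when the 2nd vaccine dose is administered". The 3-month form records the dose-2 date on the line above the draw date.

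**Analysis.** Section 11.7 analyses percent change from baseline to one month post-immunization. It does not define that time from the dose-2 date, and it does not say what happens to an off-time sample. No sampling window is stated for either draw.

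**The concern.** The Visit 4 sample carries the primary endpoint. The visit list and the Schedule of Events are the text a coordinator schedules from, and the other sites are to follow the same procedure as the lead site. A site that books from the printed days instead of the dose-2 date would sample a subject with a late second dose sooner after that dose than the endpoint specifies. The plan itself treats time since vaccination as meaningful, since it separates a short-term from a sustained response.

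The analysis would not correct for this. The only adjustment in Section 11.7 is for imbalances in baseline characteristics, and days since dose 2 is not one. The four groups are not randomized, so the timing of dose 2 could differ between them. The documents do not say whether it will.

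**Working it through.** **Inputs.** Dose 2 on Day d, from 60 to 180 (Section 9, Schedule of Events). Printed draws on Days 90 and 240 and call on Day 72 (same places). Endpoints at 1 and 6 months after dose 2 (Sections 4.2.1 and 4.2.2). Assumptions: 30-day months, and dose 1 on Day 0.

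**Step 1: reproduce the stated participation range.** If the last draw moves with dose 2, participation is 2 + 6 = 8 months to 6 + 6 = 12 months, as Section 9 states. If the last draw is fixed at Day 240, it is 240/30 = 8.0 months for everyone. The upper end needs Day 180 + 180 = Day 360, and 360/30 = 12.0 months. The stated range therefore holds only if Visit 5 moves with dose 2.

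**Step 2: compare the printed days with the endpoints.** Time from dose 2 to the printed draws is 90 − d and 240 − d. Draws that meet the endpoints fall on d + 30 and d + 180. Both printed days are early by (d + 30) − 90 = (d + 180) − 240 = d − 60.

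| Dose 2 (Day d) | 90 − d | 240 − d | Days that meet the endpoints | Printed days early by | Last visit, (d + 180)/30 |
|---|---|---|---|---|---|
| 60 | 30 | 180 | 90 / 240 | 0 | 8.0 months |
| 90 | 0 | 150 | 120 / 270 | 30 | 9.0 months |
| 120 | −30 | 120 | 150 / 300 | 60 | 10.0 months |
| 180 | −90 | 60 | 210 / 360 | 120 | 12.0 months |

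A negative value means that the printed day comes before dose 2. For the one-month draw this happens for any dose 2 after Day 90. For the phone call (72 − d) it happens for any dose 2 after Day 72.

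**Step 3: separate the two draws.** If visit order is kept, Visit 4 cannot precede Visit 3. A Day 90 draw is then possible only for d from 60 to 90, and it is at most 30 days early. Visit 5 on Day 240 follows dose 2 for every allowed d, and could be up to 120 days early without any visit being out of order.

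**Step 4: how far does near Day 60 reach?** No window is stated, so this is a range under assumed windows of ±w days around 30 days. |90 − d − 30| ≤ w gives d ≤ 60 + w, so the printed Day 90 fits for dose 2 up to:
- Day 67 (w = 7)
- Day 74 (w = 14)
- Day 90 (w = 30)

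**Step 5: the Day 0 assumption.** A subject who needs serology may receive dose 1 at about Day 7. Two months later is then Day 67, and the printed draws fall 90 − 67 = 23 and 240 − 67 = 173 days after dose 2. For such subjects the printed days are a week early even at the shortest interval.

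**The case against.** The best reply is that this is a nominal timetable with a qualifier left out. Every printed day is approximate and fits dose 2 at Day 60. Section 9 ties duration to the dose-2 date and names Visit 4 by its place after immunization. The contacts are numbered in order, and the 3-month form puts the dose-2 date next to the draw date. A draw before dose 2 is therefore unlikely, and it would be seen. The study is also a pilot sized by feasibility, with exploratory analyses (Section 11.6).

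Much of this stands. Draws timed from dose 2 were probably intended, and the larger shortfalls for Visit 4 would require visits out of order. The supporting text is also uneven: Section 4.1 puts the later time at 6 months after vaccination without naming the second dose, the sustained T-cell outcome in Section 4.2.2 is loosely worded, and Sections 2, 5 and 6.1 do not define post-immunization.

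It does not remove the point. An approximate day would have to stretch by as much as 120 days, while the same list writes out an explicit extension where one is meant. A coordinator should not have to infer the timing of the primary sample from sentences about gift cards and study duration. The exploratory aim does not help either, since estimates meant to inform later studies need a defined time point.

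**Conclusion.** The concern holds as an internal inconsistency that should be fixed. The printed days agree with the endpoints only for dose 2 near Day 60, and a fixed Day 240 contradicts the 12-month upper limit in Section 9. Across the allowed range the printed days are 0 to 120 days early. With visits in order, that is at most 30 days for the primary-endpoint draw and up to 120 days for the later one.

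These figures describe the printed days and do not predict conduct. They rest on 30-day months and dose 1 on Day 0. The window results rest on assumed tolerances. No sample-size or power figure depends on this point.

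**What to change.** **Section 9 and the Schedule of Events.** State the Visit 4 and Visit 5 draws as 1 and 6 months (about 30 and 180 days) after the actual dose-2 date. Keep Days 90 and 240 as nominal values for dose 2 at about Day 60. A sampling window for each draw would be a useful addition. Reconcile the Day 72 call, here and in Section 10.2, with the allowed dose-2 dates; no offset is proposed. Align the fixed month-3 and month-8 labels in Sections 4.2.2, 10.2 and 11.3 and on the forms.

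**Section 11.7.** Define the post-immunization time points from the dose-2 date. Derive days since dose 2 from the dose-2 date on the 3-month form and the draw dates on the 3-month and 8-month forms, linked by study ID. State that a sample taken before dose 2 is not a post-immunization value. A sensitivity analysis of off-time samples is optional.

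**Cost.** Wording changes and one derived variable from dates already collected. No visit or sample is added, the vaccine schedule is untouched, and participation of up to 12 months is already in Section 9.

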10.1 Definitions

The following definitions will be used in the assessment of safety:

Adverse Event (AE) is any untoward or unfavorable medical occurrence in a human subject, including any abnormal sign (for example, abnormal physical exam or laboratory finding), symptom, or disease,

temporally associated with the subject's participation in the research, whether or not considered related to the subject's participation in the research.

Serious Adverse Event (SAE) is any adverse event that

- (1) results in death;
- (2) is life-threatening;
- (3) results in inpatient hospitalization or prolongation of existing hospitalization;
- (4) results in a persistent or significant disability/incapacity;
- (5) results in a congenital anomaly/birth defect; or
- (6) based upon appropriate medical judgment, may jeopardize the subject's health and may require medical or surgical intervention to prevent one of the other outcomes listed in this definition (examples of such events include allergic bronchospasm requiring intensive treatment in the emergency room or at home, blood dyscrasias or convulsions that do not result in inpatient hospitalization, or the development of drug dependency or drug abuse).

Life-threatening means that the event places the subject at immediate risk of death from the event as it occurred.

Unanticipated Problem is defined as an event, experience or outcome that meets **all three** of the following criteria:

- is unexpected; AND
- is related or possibly related to participation in the research; AND
- suggests that the research places subjects or others at a greater risk of harm (including physical, psychological, economic, or social harm) than was previously known or recognized.

Possibly related means there is a reasonable possibility that the incident, experience, or outcome may have been caused by the procedures involved in the research

Unexpected means the nature, severity, or frequency of the event is not consistent with either:

- the known or foreseeable risk of adverse events associated with the procedures involved in the
 research that are described in (a) the protocol—related documents, such as the IRB-approved
 research protocol, any applicable investigator brochure, and the current IRB-approved informed
 consent document, and (b) other relevant sources of information, such as product labeling and
 package inserts; or
- the expected natural progression of any underlying disease, disorder, or condition of the subject(s) experiencing the adverse event and the subject's predisposing risk factor profile for the adverse event.

